### **5.3. Screening/Baseline/Run-in Failures**

Screen failures are defined as subjects who consent to participate in the clinical trial but are never subsequently randomized. In order to ensure transparent reporting of screen failure subjects meet the Consolidated Standards of Reporting Trials (CONSORT) publishing requirements, and respond to queries from Regulatory authorities, a minimal set of screen failure information is required including Demography, Screen Failure details, Eligibility Criteria, and Serious Adverse Events.

Any subject who receives DHA-PQP but is not subsequently randomized to blinded study treatment will be deemed a Screen Failure.

### **5.4. Withdrawal/Stopping Criteria**

A subject may withdraw from the study or discontinue study treatment at his/her own request, or may be withdrawn at any time at the discretion of the investigator for safety, behavioural or administrative reasons. If a subject withdraws from the study, he/she may request destruction of any samples taken, and the investigator must document this in the site study records.

#### **Premature Study Withdrawal**

A subject is considered to be withdrawn prematurely from the study if they do not complete the Day 180 assessment. Subjects may be prematurely discontinued from the study for any of the following reasons:

- Adverse event
- Protocol deviation
- Study closed/terminated

- Loss to follow-up
- Consent withdrawal
- Subject or investigator non-compliance
- At the request of the subject, investigator, or sponsor

Subjects are not obligated to state the reason for withdrawal from this study. However, the reasons for withdrawal, or failure to provide a reason, must be documented by the investigator on the Completion/Withdrawal section of the electronic Case Record Form (eCRF). If a subject is withdrawn from the study for any reason, the investigator should make every effort to perform the study evaluations as specified in the Time and Events table for the Withdrawal visit as applicable.

### **Premature Withdrawal of Study Treatment**

If a subject prematurely discontinues from study treatment for any reason or reaches the primary endpoint of relapse, they should continue to attend study visits to Day 180. The reason for withdrawal from treatment should be recorded in the electronic case record form (eCRF). Given the long half life of tafenoquine, the maximal pharmacodynamic effects such as potential hemolysis or methemoglobinemia may occur several days after completion of dosing. These data will be recorded, as they comprise an essential evaluation that needs to be done before discharging any subject from the study. Therefore, the investigator should continue following subjects for all protocol assessments, up to and including Day 180 whenever possible. The subject should be given appropriate rescue therapy according to local treatment guidelines if they develop a malarial recurrence (see Section 6.9.1.2).

Subjects should discontinue taking study treatment if they meet **any** of the criteria below:

- Intolerable AEs:
  - Any grade 4 AE or toxicity in the absence of compelling evidence that the AE is not related to investigational product(s)
- Clinically significant laboratory results considered by the investigator to warrant withdrawal from the study treatment
- Liver chemistry stopping criteria (refer to Section 5.4.1 and Section 12.2 Appendix 2)
- Hemoglobin stopping criteria: Given the hemolytic potential of TQ and PQ in subjects with G6PD deficiency, study specific hematologic stopping criteria will be employed (refer to Section 5.4.2)
- QTc stopping criteria (refer to Section 5.4.3)

When QT or hemolytic stopping criteria are met, this must be promptly reported by the investigator to GSK as a Serious Adverse Event (see Section 7.5)

**Subjects Lost to Follow Up**

The following actions must be taken in relation to a subject who fails to attend the clinic for a required study visit:

[figure not shown]
- The site must attempt to contact the subject and re-schedule the missed visit as soon as possible.
- The site must counsel the subject on the importance of maintaining the assigned visit schedule and ascertain whether or not the subject wishes to and/or should continue in the study.
- In cases where the subject is deemed ‘lost to follow up’, the investigator or designee must make every effort to regain contact with the subject (where possible, 3 telephone calls and if necessary a certified letter to the subject’s last known mailing address or local equivalent methods). These contact attempts should be documented in the subject’s medical record.
- Should the subject continue to be unreachable, only then will he/she be considered to have withdrawn from the study with a primary reason of “Lost to Follow-up”.

**5.4.1. Liver Chemistry Stopping Criteria**

**Liver chemistry stopping and increased monitoring criteria** have been designed to assure subject safety and evaluate liver event etiology (in alignment with the FDA premarketing clinical liver safety guidance).

[figure not shown]
<http://www.fda.gov/downloads/Drugs/GuidanceComplianceRegulatoryInformation/Guidances/UCM174090.pdf>

**Phase III-IV Liver Chemistry Stopping and Increased Monitoring Algorithm**

As blinded tafenoquine study treatment is administered as a single dose, the above criteria for stopping medication do not apply. However, the liver safety required actions and follow up assessments must be followed if the stopping criteria are met – see [Appendix 2](#) (Section 12.2). The liver safety follow-up assessments will be carried out by a local commercial laboratory where possible. If assessments are not available in Indonesia, samples will be stored in Indonesia until such time as a Material Transfer Agreement (MTA), if necessary, is formally approved for the transfer of the sample to the designated laboratory for analysis.

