**5.4.1.1. Study Treatment Restart or Rechallenge**

Study treatment restart or rechallenge after liver chemistry stopping criteria are met, are not allowed by any subject participating in this study.

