#### 5.4.2. Hemoglobin Stopping Criteria

Blinded study treatment will be stopped immediately in any subject who meets the protocol-defined criteria for Hb drop (See Section 7.5.1.1) AND has EITHER clinical evidence of hemolysis OR laboratory evidence of hemolysis based on an assessment of the tests listed below. These laboratory tests will be performed immediately once a protocol-defined Hb drop is noted by the investigator.

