### **5.4.3. QTc Stopping Criteria**

Study treatment will be stopped if any of the following criteria are met:

- QTcF >500 msec
- Uncorrected QT >600msec

These criteria should be based on the average QTcF value of triplicate ECGs. For example, if an ECG demonstrates a prolonged QTcF interval, two more ECGs should be obtained over a brief period, and then the averaged QTcF values of the three ECGs should be used to determine whether the subject should then be discontinued from the study. ECG monitoring during the following 24-48 hours should be applied for subjects found to have a prolongation to this extent.

For subjects with underlying bundle-branch block, the criteria is QTcF  $\geq$ 530msec.

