### Phase III-IV liver chemistry stopping criteria and required follow up assessments

Liver Chemistry Stopping Criteria - Liver Stopping Event	
ALT-absolute	ALT ≥ 8xULN
ALT Increase	ALT ≥ 5xULN but <8xULN persists for ≥2 weeks ALT ≥ 3xULN but <5xULN persists for ≥4 weeks
Bilirubin	ALT ≥ 3xULN and bilirubin ≥ 2xULN (>35% direct bilirubin)
INR^2	ALT ≥ 3xULN and INR>1.5, if INR measured
Cannot Monitor	ALT ≥ 5xULN but <8xULN and cannot be monitored weekly for ≥2 weeks ALT ≥ 3xULN but <5xULN and cannot be monitored weekly for ≥4 weeks
Symptomatic	ALT ≥ 3xULN associated with symptoms (new or worsening) believed to be related to liver injury or hypersensitivity
Required Actions and Follow up Assessments following ANY Liver Stopping Event	
Actions	Follow Up Assessments

 
Immediately discontinue study treatment
 
Report the event to GSK within 24 hours
 
Complete the liver event CRF and complete an SAE data collection tool if the event also meets the criteria for an SAE
 
Perform liver event follow up assessments
 
Monitor the subject until liver chemistries resolve, stabilize, or return to within baseline (see MONITORING below)
 
Do not restart/rechallenge subject with study treatment unless allowed per protocol and GSK Medical Governance approval is
 
	
 
Viral hepatitis serology
 
Only in those with underlying chronic hepatitis B at study entry (identified by positive hepatitis B surface antigen) quantitative hepatitis B DNA and hepatitis delta antibody.
 
Blood sample for pharmacokinetic (PK) analysis, obtained as soon as possible and within 24 hours of last dose, if liver event occurs within 60 days post-dose.
 
Serum creatine phosphokinase (CPK) and lactate dehydrogenase (LDH).
 

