
granted
 
 
If restart/rechallenge not allowed or not granted, permanently discontinue study treatment and may continue subject in the study for any protocol specified follow up assessments
 
 
MONITORING:
 
For bilirubin or INR criteria:
 
 
Repeat liver chemistries (include ALT, AST, alkaline phosphatase, bilirubin) and perform liver event follow up assessments within 24 hrs
 
Monitor subjects twice weekly until liver chemistries resolve, stabilize or return to within baseline
 
A specialist or hepatology consultation is recommended
 
 
For All other criteria:
 
 
Repeat liver chemistries (include ALT, AST, alkaline phosphatase, bilirubin) and perform liver event follow up assessments within 24-72 hrs
 
Monitor subjects weekly until liver chemistries resolve, stabilize or return to within baseline
 
	
 
Fractionate bilirubin, if total bilirubin <math>\geq 2 \times \text{ULN}</math>
 
Obtain complete blood count with differential to assess eosinophilia
 
Record the appearance or worsening of clinical symptoms of liver injury, or hypersensitivity, on the AE report form
 
Record use of concomitant medications on the concomitant medications report form including acetaminophen, herbal remedies, other over the counter medications.
 
Record alcohol use on the liver event alcohol intake case report form
 
 
For bilirubin or INR criteria:
 
 
Anti-nuclear antibody, anti-smooth muscle antibody, Type 1 anti-liver kidney microsomal antibodies, and quantitative total immunoglobulin G (IgG or gamma globulins).
 
Serum acetaminophen adduct HPLC assay (quantifies potential acetaminophen contribution to liver injury in subjects with definite or likely acetaminophen use in the preceding week [James, 2009]). NOTE: not required in China
 
Liver imaging (ultrasound, magnetic resonance, or computerised tomography) and /or liver biopsy to evaluate liver disease; complete Liver Imaging and/or Liver Biopsy CRF forms.
 

--	--

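### Section 5.4.1 sets aside the liver criteria for stopping medication because tafenoquine is a single dose, but that reason does not cover the 14-day blinded capsule taken in every arm

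*Protocol*

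**What the plan says.** Protocol Section 5.4.1 introduces the liver stopping and monitoring algorithm and then states: "As blinded tafenoquine study treatment is administered as a single dose, the above criteria for stopping medication do not apply". The next sentence reads: "However, the liver safety required actions and follow up assessments must be followed if the stopping criteria are met", with a reference to Appendix 2.

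Four other places bear on the same decision:

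- **Section 5.4, Premature Withdrawal of Study Treatment.** Participants who meet any item on a list should discontinue study treatment. One item is "Liver chemistry stopping criteria (refer to Section 5.4.1", which also cites Appendix 2.
- **Section 5.4.1.1.** "Study treatment restart or rechallenge after liver chemistry stopping criteria are met, are not allowed".
- **Section 12.2, Appendix 2.** The first action after any liver stopping event is "Immediately discontinue study treatment". Where restart is not allowed, the site is to "permanently discontinue study treatment and may continue subject in the study for any protocol specified follow up assessments". The footnote on bilirubin fractionation also orders discontinuation at ALT of at least 3xULN with bilirubin of at least 2xULN if fractionation is not immediately available.
- **Sections 4.2 and 6.** Blinded study treatment covers tafenoquine, primaquine and both placebos. Every arm takes one blinded capsule daily for 14 days, starting on Day 1 or Day 2.

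**The concern.** The only reason given for setting the criteria aside is that tafenoquine is given once. That is true of the two tablets and untrue of the capsule, which is active primaquine in one arm of three. Because the design is double-dummy, the site cannot tell whose capsules are active.

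Section 5.4.1 is where an investigator would look first when an ALT result comes back high, and Section 5.4 sends the reader there. Someone who acts on its first statement could order every follow-up test and still hand over the next capsule. What is at stake is participant safety in a small number of possible cases, not the efficacy comparison.

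**Working it through.** There is no sample-size or power figure to reproduce. The check is a comparison of texts followed by a count of capsules.

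**Step 1: the texts side by side.**

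| Place | What it tells the site once a liver stopping criterion is met | Relation to the 5.4.1 sentence |
|---|---|---|
| 5.4.1, first statement | Criteria for stopping medication are not applicable | n/a |
| 5.4.1, next statement | Carry out the Appendix 2 actions | Brings back the stop indirectly, since stopping is the first action |
| 5.4 list | Discontinue study treatment | Direct conflict |
| Appendix 2 actions and bilirubin footnote | Discontinue study treatment, immediately under the action list | Direct conflict |
| 5.4.1.1 | No restart | Indirect: presupposes a stop |

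The two sibling rules make no exception for single dosing, although tafenoquine is the same single dose there. Section 5.4.2 says "Blinded study treatment will be stopped immediately in any subject who meets the protocol-defined criteria for Hb drop" (with evidence of hemolysis), and Section 5.4.3 says "Study treatment will be stopped if any of the following criteria are met". They do not contradict 5.4.1, but they show that the protocol elsewhere treats the blinded course as something that can be stopped.

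**Step 2: which liver criteria can be met while capsules remain.** Those that act at once: ALT of at least 8xULN; ALT of at least 3xULN with the bilirubin condition, with INR above 1.5 if measured, or with symptoms; and ALT of at least 3xULN that cannot be monitored weekly. The last is remote, given daily visits and a 24-hour clinic. The persistence criteria (2 or 4 weeks) do not matter here: two weeks from the first post-baseline scheduled test on Day 3 is Day 17, after the last capsule on Day 14 or 15.

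**Step 3: capsules left.** Inputs:

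- 14 capsules of 15 mg (Sections 4.2 and 6), so a full course is 14 x 15 = 210 mg.
- Start on Day 1 or Day 2 (Section 7.1, note a).
- Scheduled post-baseline chemistry during dosing on Days 3, 5, 7 and 14 (Section 7.1).
- Result lag of 0 or 1 day. This is an assumption: the protocol gives no turnaround time, though Section 7.2 allows for screening chemistry to be pending.

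Counting after the capsule of the day on which the result is in hand:

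capsules left = 14 − min(14, test day + lag − start day + 1)

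| Lag, start | Day 3 | Day 5 | Day 7 | Day 14 |
|---|---|---|---|---|
| 0, Day 1 | 11 | 9 | 7 | 0 |
| 0, Day 2 | 12 | 10 | 8 | 1 |
| 1, Day 1 | 10 | 8 | 6 | 0 |
| 1, Day 2 | 11 | 9 | 7 | 0 |

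For Days 3, 5 and 7 the range is 6 to 12 capsules. In the primaquine arm this is 6 x 15 = 90 mg to 12 x 15 = 180 mg, or 90/210 = 43% to 180/210 = 86% of the course. After a Day 14 test at most one capsule remains.

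**The case against.** The strongest reply is that the protocol already settles the matter. The sentence that follows makes the Appendix 2 actions mandatory, and the first of them is to stop. Section 5.4 says the same. This stands, and it rules out the stronger reading that a reader might infer, namely that the trial has no liver stopping rule or has switched it off. The documents do not support that.

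A second reply is that the sentence names tafenoquine, so it may concern only the tablets, for which stopping after a single dose is meaningless. That is probably the intent. But nothing limits the second half of the sentence to the tablets, and Section 5.4.1 never states the rule for the capsule. Opening the next sentence with a contrast also invites a site to do the tests without stopping.

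A third reply is that the algorithm figure in Section 5.4.1 is not visible in the text reviewed. The criteria referred to are therefore taken to be those in Appendix 2. The conflict with Section 5.4 and Appendix 2 does not depend on the figure.

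A fourth is that the capsule count exaggerates. It is indeed a ceiling, not an expected exposure. Every dose is supervised, stopping events go to the sponsor within 24 hours, and repeat chemistry follows within 24 to 72 hours at most. Section 5.4 also stops treatment for grade 4 toxicity without compelling evidence that it is unrelated, and for laboratory results that the investigator judges to warrant it. Any of these could end dosing early.

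**Conclusion.** The point holds as an internal contradiction in a safety rule. One sentence in Section 5.4.1 says the reverse of what Section 5.4 and Appendix 2 require, for a reason that does not cover the 14-day capsule. The conflict with Section 5.4.1.1 is indirect only.

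The size is bounded. At most 6 to 12 capsules could follow a stopping event found on Day 3, 5 or 7, which is 90 to 180 mg of primaquine in the one arm of about 50 where the capsule is active. That assumes a result lag of 0 or 1 day and that the site gives the whole remaining course. The documents give no event rate. The event is probably rare, since ALT above 2xULN is excluded at entry.

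A reader might also infer damage to the trial's result. The mITT analysis in the SAP keeps participants in their randomised group whether or not they discontinue treatment, so the primary comparison is not affected. The one analysis link is SAP Appendix 1, per-protocol exclusion 06, which turns on the Section 5.4 withdrawal criteria. A participant who met a liver criterion and kept taking capsules would be excluded there, although the site could say it had followed Section 5.4.1.

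**What to change.** Replace the sentence in Section 5.4.1 with:

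> The single dose of TQ or TQ placebo cannot be withdrawn once given; if a liver stopping criterion is met, all remaining blinded PQ or PQ-placebo capsules must be stopped immediately and not restarted, as required by Section 5.4 and Appendix 2.

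Keep the following sentence on the Appendix 2 actions, but drop its opening contrast word.

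Do not add a new instruction on DHA-PQP here. An order to stop it after a Day 3 result could remove the last blood-stage dose, and Section 5.4 provides rescue therapy only for a recurrence. Leave DHA-PQP to Appendix 2. If it is mentioned, state that alternative blood-stage treatment is given when it is stopped before the third dose.

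The cost is one replaced sentence and one deleted word. Sample size, visit schedule and analyses do not change.

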**Phase III-IV Liver Chemistry Increased Monitoring Algorithm with Continued Therapy for ALT ≥3xULN but <8xULN**

Liver Safety Required Actions and Follow up Assessments Section can be found in [Appendix 2](#) (Section 12.2).

**5.4.1.1. Study Treatment Restart or Rechallenge**

Study treatment restart or rechallenge after liver chemistry stopping criteria are met, are not allowed by any subject participating in this study.

#### 5.4.2. Hemoglobin Stopping Criteria

Blinded study treatment will be stopped immediately in any subject who meets the protocol-defined criteria for Hb drop (See Section 7.5.1.1) AND has EITHER clinical evidence of hemolysis OR laboratory evidence of hemolysis based on an assessment of the tests listed below. These laboratory tests will be performed immediately once a protocol-defined Hb drop is noted by the investigator.

##### Hematology

- Hemoglobin
- Hematocrit
- Platelets
- WBC
- RBC
- Reticulocytes

##### Clinical Chemistry

- Creatinine
- BUN
- Total bilirubin
- Indirect bilirubin
- AST
- ALT
- Alkaline phosphatase
- CPK
- LDH
- Visual inspection of urine and dipstick

Subjects will also be required to have a repeat G6PD quantitative phenotype test to confirm that they are not G6PD deficient. G6PD genotyping may be performed if repeat phenotyping would not define G6PD status (e.g. transfusion given or high reticulocyte count).

### **5.4.3. QTc Stopping Criteria**

Study treatment will be stopped if any of the following criteria are met:

- QTcF >500 msec
- Uncorrected QT >600msec

These criteria should be based on the average QTcF value of triplicate ECGs. For example, if an ECG demonstrates a prolonged QTcF interval, two more ECGs should be obtained over a brief period, and then the averaged QTcF values of the three ECGs should be used to determine whether the subject should then be discontinued from the study. ECG monitoring during the following 24-48 hours should be applied for subjects found to have a prolongation to this extent.

For subjects with underlying bundle-branch block, the criteria is QTcF  $\geq$ 530msec.

### **5.5. Subject and Study Completion**

A completed subject is one who has been randomized to blinded study treatment and has a day 180 assessment.

The end of the study is defined as the last subject's last visit.

## 6. STUDY TREATMENT

‘Blinded study treatment’ refers to tafenoquine, primaquine and the corresponding placebos.

	Study Treatment				
Product name:	Tafenoquine (SB-252263)	Matched-Placebo for Tafenoquine	Primaquine	Matched-Placebo for Primaquine	DHA-PQP 320/40 dihydroartemisinin-piperaquine
Formulation description:	Each tablet will contain 150mg tafenoquine	Each tablet will contain tafenoquine matched-placebo	Each over-encapsulated tablet will contain 15mg primaquine	Each capsule will contain primaquine matched-placebo	Each tablet will contain 320mg piperaquine tetrasphosphate (as the tetrahydrate;PQP) and 40mg dihydroartemisinin (DHA)
Unit dose strength(s) /Dosage level(s):	150 mg tafenoquine	Placebo	Equivalent to 15mg primaquine base	Placebo	Equivalent to 40mg DHA and 320 PQP base
Route of Administration:	Administer orally	Administer orally	Administer orally	Administer orally	Administer orally
Dosing instructions:	Administer 2 tablets with water as a single dose after a meal. Dose to be taken at least 3 hours after DHA-PQP	Administer 2 tablets with water as a single dose after a meal. Dose to be taken at least 3 hours after DHA-PQP	Administer 1 capsule daily with water as a single dose after a meal for 14 days. Dose to be taken at least 3 hours after DHA-PQP (Days 1, 2 and 3).	Administer 1 capsule daily with water as a single dose after a meal for 14 days. Dose to be taken at least 3 hours after DHA-PQP (Days 1, 2 and 3).	Single dose for 3 days  3 tablets per day for subjects <75Kg  4 tablets per day for subjects ≥75Kg  Dose to be taken at least 3 hours after last food intake. No food to be taken for at least 3 hours after dosing

### 6.1. Treatment Assignment

Subjects will be assigned to one of three blinded treatment arms: DHA-PQP alone, DHA-PQP plus TQ or DHA-PQP plus PQ in accordance with the randomization schedule generated by Clinical Statistics, prior to the start of the study, using validated internal software.

Subjects will be randomized via an interactive web recognition system (IWRS) to blinded study treatment after beginning administration of open label DHA-PQP. Each subject scheduled to receive blinded study treatment will receive a treatment allocation number (i.e. randomization number) via the IWRS system on Day 1. The treatment allocation

ratio will be 1:1:1. Once a randomization number has been allocated to a subject, it cannot be re-assigned to any other subject.

Open label DHA-PQP will be administered daily over three consecutive days. Each dose will be taken at least 3 hours after the last food intake and no food will be taken for 3 hours after each dose. If a subject vomits within 30 minutes of taking DHA-PQP on Days 1 to 3, the whole dose should be re-administered; if the subject vomits within 30-60 minutes, half the dose should be re-administered. Repeat dosing with DHA-PQP should not be attempted more than once. If the repeat dose is vomited on Day 1, the subject should be withdrawn from the study and given appropriate rescue medication as outlined in Section 6.9.1.2.

Blinded study treatment will be administered daily over 14 days together with food (at least 3 hours after dosing with DHA-PQP on Days 1, 2 and 3). If the subject vomits within 1 hour following dosing, a repeat dose should be given. If the repeat dose is vomited on Day 1, the subject should be withdrawn from the study and given appropriate rescue medication as outlined in Section 6.9.1.2.

